Cover Page

Official Study Title: Safety of Immediate Skin-To-Skin Contact after Vaginal Birth in Vigorous Late-Preterm Neonates – A Pilot Study

NCT Number: 03585192

Protocol Date: October 24, 2017

Date of Document: August 21, 2018

Protocol

I. Inclusion Criteria

1. Singletons born 35 0/7 to 36 6/7 weeks GA via vaginal delivery
2. Vigorous - crying, good respiratory effort, good tone
3. No major congenital malformation

II. Recruitment

1. Recruitment will occur at UH MacDonald Women's Hospital.
2. Mothers who meet the inclusion criteria will be tracked in the EMR at time of admission to the Labor & Delivery Unit.
3. Informed consent will be obtained by members of the research team.
 - a. Consenting process will occur at the time of Mother's admission to the Labor & Delivery Unit.
 - b. Consent will be obtained in Mother's room.
 - c. Mother will not be consented if sedated, under distress from laboring process, or clinically unstable per Labor & Delivery Team.

III. Randomization

1. Index cards with **skin** or **warmer** written on them will be placed in opaque, sealed envelopes.
2. The envelopes will be shuffled randomly and numbered 1-120. The envelopes will be kept in chronological order. Extra envelopes containing index cards will be made if needed using the same randomized process. The investigators anticipate needing approximately 30% more randomized envelopes than what has been calculated by our Statistician due to unplanned deliveries in which the Mother was planning to have a vaginal birth and needs to undergo a cesarean section, either the Mother or neonate are unstable after delivery, or Mother's decision to withdrawal from the study. In the event of the above scenarios, an additional Mother-neonate dyad will need to be randomized in order to achieve our goal of 92 neonates for study completion.
3. Envelopes will be stored in the Neonatal Treatment Room adjacent to Operation Room 1 on the Labor & Delivery Unit.
4. After obtaining informed consent and if the Mother is agreeable to participate in this study, a sealed envelope will be brought to laboring room and opened prior to delivery. No one in the delivery room will know what is written on the index card. The envelope will be opened right before delivery.
5. Skin is the intervention group (Group 1) and warmer is the control group (Group 2)
6. **Skin (Group 1)**
 - a. If the newborn is vigorous (crying, good respiratory effort, good tone) after vaginal delivery, newborn will be able to go directly to Mother's chest for immediate SSC
 - b. A pulse oximeter will be placed on the newborn's right wrist. Saturations will be monitored on a pulse oximeter located next to the Mother's bed.

7. **Warmer (Group 2)**
 - a. Newborn will go to the radiant warmer, pulse oximeter placed on newborn's right wrist, and saturations will be monitored on the Panda Warmer.
 - b. If stable per Baby RN after 20 minutes of observation, the newborn will be placed on Mother's chest for SSC.
8. In the event that the Mother agrees to the study and is randomized into the control group but requests SSC, Mother will be informed that UH standard of care does not allow this practice for late-preterm neonates outside of this study and the Mother is free to stop participation in the study at any time.
9. Information about how the newborn transitioned after birth will be collected, regardless if neonate is in the skin or warmer group. The information gathered will be analyzed to determine if there are any differences in postnatal transitioning between the two groups of newborns.

IV. Study Methods

Preparation prior to vaginal delivery (all late-preterm neonates)

1. Prepare Mother to receive newborn (bra removed & uncover breasts)
2. Place warm blanket on Mother's abdomen to receive neonate.
3. Pulse oximeter will be turned on and placed bedside to allow uninterrupted contact and positioning between Mother and neonate. Screen is to be visible to Labor & Delivery RN at all times.

Initiate immediate SSC after vaginal birth of vigorous late-preterm neonate – Group 1 (skin)

1. Newborn Nurse will assist Mother with initiating skin-to-skin contact
2. Place nude neonate supine on warm blanket on Mother's abdomen
3. Suction mouth and nose if necessary, dry, & remove wet blanket
4. Place pulse oximeter on right upper extremity, hat, diaper, and cover with warm receiving blanket
5. Assign 1 minute APGAR
6. Any change in clinical status of either Mother (based on clinical judgment by OB Physician or Midwife) or neonate (based on clinical judgment by Pediatric Team or Neonate's RN) will preclude continued SSC and warrant immediate intervention until stabilized.
 - a. Interventions to stabilize neonate: repositioning on Mother's chest, ensure unobstructed airway, oral suctioning with bulb syringe if needed, reapply pulse oximeter, & remove from Mother's chest if needed.

Monitoring during postnatal transitioning

Following standard of care, there is a dedicated baby RN that will be continuously assessing the baby in a location consistent with current UH Clinical Practice Guidelines. Routinely, any baby doing SSC is not placed on continuous pulse oximetry. However, for the purposes of this study, we will place all babies (control and experimental groups) on continuous pulse oximetry to ensure safety with SSC. The pulse oximeter will record continuous oxygen saturation and heart rate.

1. Following current standard of care, after drying and stimulating with warm blanket, remove the wet blanket, and place neonate in prone position on Mother's bare chest between breasts in upright position within 5 minutes of birth
2. Monitor neonate's head position and ensure nose is unobstructed
3. Cover with 2-4 layers of warm receiving blankets
4. Assign 5 minute APGAR
5. Neonate to stay on Mother's chest for uninterrupted SSC for at minimum first 60 minutes of life irrespective of timing of first feed. The goal is continuous, monitored SSC within the first 60 minutes of life.
6. Routine vital signs, including pulse oximetry, will be monitored and documented in the EMR until Mother/neonate stable for transfer to antepartum unit. Vital signs will be obtained per current UH protocol (see attachment – Clinical Practice Guideline Care of the Well Neonate). Normal values and assessment data include:
 - a. Axillary temperature 36.5-37.5 degrees Celsius
 - b. Heart rate of 100 to 180 beats per minute (if not eating or crying)
 - c. Regular cardiac rhythm
 - d. Respiratory rate of 40-60 breaths per minute
 - e. Pulse oximetry parameters per NRP guidelines (see attachment – Foundations of Neonatal Resuscitation).
 - f. Any pulse oximetry reading < 85% after 10 minutes of life will require the baby to be repositioned on Mother's chest, ensure unobstructed airway, oral suctioning with bulb syringe if needed, reapply pulse oximeter, & remove from Mother's chest if needed.
 - g. Any pulse oximetry reading < 88% at 1 hour of life will require the baby to be repositioned on Mother's chest, ensure unobstructed airway, oral suctioning with bulb syringe if needed, reapply pulse oximeter, & remove from Mother's chest if needed.
 - h. Screening and management of postnatal glucose homeostasis will be instituted, as is the current policy at UH MacHouse Women's Hospital, for all late-preterm neonates until 24 hours of life (see attachment – University Hospitals MacDonald Women's Hospital Screening and Management of Postnatal Glucose Homeostasis).
7. Signs of tolerance of postnatal SSC:
 1. Pink or with mild acrocyanosis
 2. Respiratory effort easy, no audible grunting, or visible intercostal retractions
 3. Alert, demonstrating feeding cues, or sleeping comfortably
 4. Well-flexed posture with good tone
8. Any change in clinical status of either Mother (based on clinical judgment by OB Physician or Midwife) or neonate (based on clinical judgment by Pediatric Team or Neonate's RN) will preclude continued SSC and warrant immediate intervention until stabilized.
 1. Interventions to stabilize neonate: repositioning on Mother's chest, ensure unobstructed airway, oral suctioning with bulb syringe if needed, reapply pulse oximeter, & remove from Mother's chest if needed.

Monitoring of late-preterm neonate if randomized to Group 2 (warmer)

1. Initial period of observation (20 minutes) under the radiant warmer per current UH protocol
2. Place pulse oximeter on right upper extremity
3. SSC protocol to be followed as detailed in **(numbers 2-8)**
4. Any change in clinical status of either Mother (based on clinical judgment by OB Physician or Midwife) or neonate (based on clinical judgment by Pediatric Team or Neonate's RN) will preclude continued SSC and warrant immediate intervention until stabilized.
 - a. Interventions to stabilize neonate: repositioning on Mother's chest, ensure unobstructed airway, oral suctioning with bulb syringe if needed, reapply pulse oximeter, & remove from Mother's chest if needed.

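### Replacing randomised dyads because the neonate is unstable after delivery, with no cut-off before assigned care starts, can take part of the safety outcome out of the count

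*Protocol*

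**What the plan says.** Section III, item 2 expects about 30% more envelopes than the calculated number, for three kinds of event: an unplanned cesarean section, the case where "either the Mother or neonate are unstable after delivery", and maternal withdrawal. For all of them the instruction is the same: "an additional Mother-neonate dyad will need to be randomized in order to achieve our goal of 92 neonates for study completion". The supply matches this: "The envelopes will be shuffled randomly and numbered 1-120".

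Item 4 of the same section fixes when the allocation becomes known: "The envelope will be opened right before delivery". Cesarean section, instability and many withdrawals can therefore occur after the arm is known.

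The inclusion criterion that can be judged only at birth is section I, item 2: "Vigorous - crying, good respiratory effort, good tone". It applies to both arms.

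Deterioration during assigned care is covered in section IV, in item 6 for Group 1 and item 4 for Group 2. In both, a change in clinical status "will preclude continued SSC and warrant immediate intervention until stabilized". Neither item mentions leaving the study or being replaced.

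The title announces the "Safety of Immediate Skin-To-Skin Contact after Vaginal Birth in Vigorous Late-Preterm Neonates", and section III, item 9 says the data are used to "determine if there are any differences in postnatal transitioning between the two groups of newborns".

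**The concern.** The replacement trigger is undefined, has no time limit and is not tied to the vigour criterion. As worded it covers two different situations:

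- **Not vigorous at birth.** The dyad fails an inclusion criterion. Not counting it is defensible if the judgement is made in the same way in both arms before assigned care starts.
- **Vigorous at birth, then unstable in the assigned setting.** This neonate was eligible and received the assigned care, and its instability is part of the postnatal transition that the trial compares.

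If the second kind is replaced and not analysed, neonates leave the comparison because of their outcome, and the decision is made by staff who can see the arm. A real excess of instability with immediate skin-to-skin contact would look smaller in absolute terms and fewer safety events would appear. In a small pilot, that favours a reading of no difference.

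**Working it through.** **The plan's own figure.** 92 × 1.30 = 119.6, rounded up to 120 envelopes, so the stated number reproduces. It provides for 120 − 92 = 28 envelopes (28/120 = 23%) for dyads that do not count towards the 92. The protocol does not say how many of these are meant for neonatal instability.

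**What the wording covers.** The protocol uses different words for two states. At birth the neonate is vigorous or not (section I, item 2; section III, item 6a). Stability mostly describes what follows: the warmer-group neonate is judged stable or not after 20 minutes of observation (section III, item 7b), and section IV has staff intervene until the neonate is stabilised. Instability after delivery, the term in section III, item 2, therefore reaches naturally into the period of assigned care. Section III, item 2 then calls for another dyad, while section IV continues to manage the first one. Neither says whether the first still counts.

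**Size, for illustration.** Only the 92 comes from the protocol. Assumptions: 46 counted per arm, a true instability rate *p* after assigned care starts, a share *f* of unstable neonates replaced (the same in both arms), and replaced neonates not analysed.

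- Observed rate = p(1 − f)/(1 − pf)
- Randomised per arm to count 46 = 46/(1 − pf); replaced = 46/(1 − pf) − 46

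| True rates, skin v warmer | f | Observed rates | Difference (points) | Risk ratio |
|---|---|---|---|---|
| 10% v 5% | 0 | 10.0% v 5.0% | 5.0 | 2.00 |
| 10% v 5% | 1/4 | 7.7% v 3.8% | 3.9 | 2.03 |
| 10% v 5% | 1/2 | 5.3% v 2.6% | 2.7 | 2.05 |
| 20% v 10% | 0 | 20.0% v 10.0% | 10.0 | 2.00 |
| 20% v 10% | 1/4 | 15.8% v 7.7% | 8.1 | 2.05 |
| 20% v 10% | 1/2 | 11.1% v 5.3% | 5.8 | 2.11 |

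Worked case, 10% v 5% with f = 1/2:

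- Observed rates: 0.05/0.95 = 0.0526 and 0.025/0.975 = 0.0256.
- Randomised: 46/0.95 = 48.42 and 46/0.975 = 47.18, so 2.42 + 1.18 = 3.60 replaced.
- Events among all randomised: 4.84 + 2.36 = 7.20. Events among those counted: 2.42 + 1.18 = 3.60.

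With f = 1/4 the replacements are 1.18 + 0.58 = 1.76.

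**Unequal replacement.** If the true rate is 10% in both arms and half of the unstable neonates are replaced in one arm only, the observed rates are 5.3% and 10.0%. That is a spurious difference of 4.7 points, in either direction depending on the arm.

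**The case against.** The strongest reply is that section III, item 2 is a rule about envelope supply. Randomising an extra dyad does not remove the first one, and 92 for completion may simply be the number at which the trial ends. Who is analysed is usually left to the SAP, which is not at hand. The narrow reading also has support. Section III, item 6a makes vigour after delivery the condition for going to the mother's chest, and instability stands next to cesarean section, the other inclusion failure that arises after consent. Section IV manages later deterioration without any exit from the study.

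Much of this stands. The narrow reading is possible, the protocol never says that replaced dyads are left out, and if they are analysed this bias does not arise. But the replacement rule is an instruction that staff act on. Nothing in it requires data collection to continue for a replaced dyad, and the SAP cannot recover data that were not collected. Section III, item 9 covers both arms but does not mention replaced dyads.

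It is also fair to say that the rates are assumed, that no binary instability endpoint is defined, and that power is low anyway. At 10% v 5% with 46 per arm, two-sided 5% power is about 15% with none replaced and about 10% with half replaced (normal approximation), so a non-significant result is likely either way. That limits what any test can show. It makes the event counts and the absolute difference, which replacement erodes, more important to the reader of a safety pilot.

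**Conclusion.** The concern holds and should be fixed; confidence is moderate. The protocol replaces randomised dyads for a neonatal state that overlaps with its safety outcome, after the arm is known and with no cut-off before assigned care starts. It does not say whether those dyads stay in the comparison.

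Harm requires that neonates already in assigned care are in fact replaced and that they are then omitted from the analysis. Under those conditions, with one quarter to one half replaced equally in both arms, an assumed 5.0-point excess would read as 3.9 to 2.7 points, and an assumed 10.0-point excess as 8.1 to 5.8 points. The loss is in the absolute excess and the number of events seen, with little change in the risk ratio. Under the narrow reading, or if replaced dyads are analysed, the loss from this source is nil.

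**What to change.** Amend section III, item 2 in three respects:

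1. A randomised dyad is not counted only if it fails an inclusion criterion (cesarean section, or not vigorous at birth under section I, item 2), judged by the same criterion in both arms before assigned care starts.
2. Every other randomised dyad stays in data collection and in the main comparison by assigned arm, as far as consent allows, whether or not an extra dyad is also randomised.
3. Every replaced dyad is logged and reported by arm and reason.

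The cost is two or three sentences and a replacement log, with no enrolment beyond the extra dyads already planned. There are two downsides. Some analysed neonates will not have had the full assigned contact, which slightly dilutes the contrast. Vigour will still be judged after the envelope is opened, so that judgement is not blind to arm, and the log by arm is needed to show any imbalance. The change concerns only who is counted; clinical management stays as it is.

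### The allocation envelope is opened before birth, so vigour, an inclusion criterion, is judged after the arm has been disclosed

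*Protocol*

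**What the plan says.** Section III, item 4 gives the time of opening twice. It first has "a sealed envelope will be brought to laboring room and opened prior to delivery", and then continues: "No one in the delivery room will know what is written on the index card. The envelope will be opened right before delivery". The statement about who knows the card stands between the two and has no time limit.

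Section I, item 2 lists as an inclusion criterion "Vigorous - crying, good respiratory effort, good tone". Item 1 of the same section requires vaginal delivery.

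The skin step (section III, item 6a) repeats vigour as a condition at the bedside: "If the newborn is vigorous (crying, good respiratory effort, good tone) after vaginal delivery, newborn will be able to go directly to Mother's chest". The warmer step (item 7a) does not repeat it: "Newborn will go to the radiant warmer, pulse oximeter placed on newborn's right wrist".

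Section III, item 2 foresees that some allocated dyads will be lost to caesarean section, to instability of mother or neonate after delivery, or to withdrawal. A further dyad is randomised for each until 92 neonates complete. Item 8 says that the hospital's standard of care does not allow the requested skin-to-skin contact for late-preterm neonates outside the study. Item 9 makes postnatal transition the comparison between the groups.

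**The concern.** Concealed allocation protects a randomised comparison only while eligibility is decided without knowledge of the arm. Here the last eligibility decision comes after the card has been read. It rests on a bedside impression of crying, breathing effort and tone. The question also presses harder in one arm: in the skin arm it decides whether the newborn goes to the chest, while the warmer step poses no such condition at that moment.

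Caution over a borderline newborn is foreseeable when the assigned practice lies outside the hospital's standard of care. If such newborns left the count more often in the skin arm and were replaced, that arm would hold healthier newborns and immediate contact would look safer than it is. This is a safety study, so an error in that direction matters most. If newborns were excluded from the data with the arm known, no later analysis could restore concealment.

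**Working it through.** **Order of events**

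1. Envelope opened in the labouring room, before delivery (section III, item 4).
2. Birth. Whether it is vaginal is now settled (section I, item 1).
3. Vigour judged (section I, item 2; section III, item 6a places it after delivery).
4. Newborn placed according to the card (section III, items 6a and 7a).
5. Dyads with an unstable mother or neonate replaced (section III, item 2).

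Steps 2, 3 and 5 all follow disclosure. The protocol names no assessor kept unaware of the arm. Those receiving the newborn must know the arm to carry out step 4.

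**The plan's own figures**

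- Envelopes: 92 × 1.30 = 119.6, rounded up to 120, as stated.
- Spare envelopes: 120 − 92 = 28, and 28/120 = 23.3%. This covers caesarean, instability and withdrawal together. It shows how much post-allocation loss is expected in total and does not measure exclusions on vigour.

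**Illustration of size**

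Only the total of 92 comes from the protocol. The assumptions are 92/2 = 46 per arm, an event risk of 0.15 in a clearly vigorous newborn, a risk r of 0.40 to 0.80 in a borderline one, and k borderline newborns replaced in the skin arm only.

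Fall in skin event rate = k × (r − 0.15)/46

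| k | r = 0.40 | r = 0.60 | r = 0.80 |
|---|---|---|---|
| 2 | 1.1 points | 2.0 points | 2.8 points |
| 5 | 2.7 points | 4.9 points | 7.1 points |

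For scale, one newborn in 46 is 2.2 points. The standard error of a difference at 15% with 46 per arm is √(2 × 0.15 × 0.85/46) = 7.4 points.

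A second route assumes the same true risk p in both arms and a share s of skin-arm events removed over and above the warmer arm. The apparent skin risk is p(1 − s)/(1 − ps). At p = 0.20 and s = 0.25 it is 0.15/0.95 = 15.8%, a spurious difference of 4.2 points. That needs 60 × 0.20 × 0.25 = 3 extra exclusions if 60 are randomised to skin. Over p = 0.10 to 0.30 and s = 0.10 to 0.50 the difference runs from 0.9 to 12.4 points. The spread shows how far the result depends on the assumptions.

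**The case against.** Much can be said for the protocol as written.

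- **The sentence on no one knowing the card.** A reader might infer that it is impossible. Its natural meaning is concealment until opening. On that reading it is true and only lacks a time limit, though it gives no protection at the vigour call.
- **Vigour in the warmer arm.** A reader might infer that no vigour call is made there. Section I, item 2 applies to the whole trial, and the silence of item 7a does not waive it. What stands is that only the skin step makes it a bedside condition.
- **Who is dropped.** A reader might infer that knowledge of the arm decides who counts. Section III, item 2 lists instability, not lack of vigour, and applies to both arms. The protocol does not say that a non-vigorous skin newborn leaves the data, and item 9 collects transition data in both groups. If every such newborn is analysed as randomised, this bias does not arise. The analysis set may be defined in a SAP, which was not available here.
- **Who makes the call.** The protocol names neither the person who opens the envelope nor the one who judges vigour. That the caller knows the arm is likely from the workflow, but it is inferred. Staff caution is also an assumption.
- **Size.** The event risks and the number replaced have no source in the document, and even the largest shift in the table is below one standard error.
- **Feasibility.** The five-minute limit in section IV is for prone placement on the chest. Group 1 handling starts earlier, on the mother's abdomen, so that limit does not by itself make room for opening an envelope after birth.

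These points limit what can be claimed about direction and size. They do not change the order of events.

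**Conclusion.** The concern holds as a design weakness. Allocation is disclosed before two inclusion criteria are settled, and one of them is subjective. Together with replacement up to 92 completers, this leaves an opening for different exclusions in the two arms. The skin arm would plausibly benefit, given section III, item 8.

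The protocol does not establish that bias occurs, that it runs in that direction, or how large it is. The shift of about 1 to 7 points rests wholly on assumed risks, an assumed 46 per arm and 2 to 5 newborns replaced in one arm only. It also depends on those newborns leaving the comparison, which the protocol does not state. The change is worth making because it is cheap and closes this route at the design stage.

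**What to change.** Amend section III, item 4 so that the envelope stays sealed until vaginal birth has occurred and vigour (yes/no, with the time) has been called and recorded, by the same criterion for every consented dyad. Open the next-numbered envelope only if the answer is yes. Replace the sentence that no one in the room will know the card with: *allocation is concealed until the vigour call is recorded*.

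Caesarean and non-vigorous births would then use no envelope. Instability after allocation and withdrawal would remain, and should be reported by arm.

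The cost is a wording amendment, one timed entry on the data sheet and a short delay between birth and allocation. The investigators must reconcile item 4 with the initial-placement steps for Groups 1 and 2, so that handling before the envelope is opened is the same in both arms. How that is done at the bedside is for them to decide.

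If they judge opening after birth unworkable, the fallback is to record vigour by the same criterion in both arms and keep every randomised, vaginally born neonate in the comparison by assigned arm. Exclusions and their reasons should be reported by arm.

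### Does the stated aim of looking for differences between the groups commit this safety pilot to reading a null result as safe?

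*Protocol*

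**What the plan says.** The cover page titles the trial "Safety of Immediate Skin-To-Skin Contact after Vaginal Birth in Vigorous Late-Preterm Neonates – A Pilot Study". Under III. Randomization, item 2 sets "our goal of 92 neonates for study completion" and attributes the calculated number to the trial's statistician, without giving the inputs. The same item says of the envelopes: "The envelopes will be shuffled randomly and numbered 1-120". Item 8 notes that "UH standard of care does not allow this practice for late-preterm neonates outside of this study". Item 9 states the analysis aim: "The information gathered will be analyzed to determine if there are any differences in postnatal transitioning between the two groups of newborns".

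Under IV. Study Methods, the part on monitoring during postnatal transitioning says "we will place all babies (control and experimental groups) on continuous pulse oximetry to ensure safety with SSC", and adds "The pulse oximeter will record continuous oxygen saturation and heart rate". The same part lists temperature, heart rate, respiratory rate and saturation limits for bedside monitoring, and glucose screening. The protocol does not present any of these limits as a criterion for comparing the groups or for concluding that the practice is safe.

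**The concern.** A safety question is directional: is immediate skin-to-skin contact worse than a period under the warmer? Item 8 sharpens this, because the practice is not otherwise permitted at this hospital for these infants. Item 9, by contrast, asks only whether the groups differ, over an open set of transition data. The answer most favourable to the intervention would be that no differences were found. In a small trial that answer has two explanations: the intervention is not worse, or there were too few neonates to tell.

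If the trial were to conclude safety from a non-significant comparison, a real increase in an uncommon adverse event could pass unnoticed and the practice could be adopted on weak evidence. That would be a serious fault, so it is worth checking whether the protocol commits it.

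**Working it through.** **The plan's own figures.** The 92 cannot be reproduced, because the protocol gives no significance level, power, effect size, standard deviation, event rate or margin. The related envelope count can: 92 × 1.30 = 119.6, rounded up to 120, which matches the stated allowance of about 30%.

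**Assumptions for what follows.** 1:1 allocation, so 46 per arm (the protocol states no ratio); two-sided 5% level; event rates chosen for illustration, since the protocol gives none.

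**Power to detect a doubled event rate.** Two methods were used: Fisher's exact test by enumerating all outcomes, and the normal approximation with power = Φ{(|p₂ − p₁| − 1.96·√[2p̄(1 − p̄)/46]) / √[(p₁(1 − p₁) + p₂(1 − p₂))/46]}, where p̄ is the mean of the two rates.

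| Warmer vs skin | Fisher | Normal |
|---|---|---|
| 5% vs 10% | 6% | 15% |
| 10% vs 20% | 18% | 27% |
| 20% vs 40% | 47% | 55% |
| 30% vs 60% | 77% | 84% |

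A doubling is missed more often than found only when the control rate is below about 18% (normal) to 21% (Fisher).

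**Two worked results.** With 10/46 events against 5/46, Fisher p = 0.26 and the Newcombe 95% interval for the difference runs from −5 to +26 points. With no events in either arm the interval is ±7.7 points.

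**Precision.** With 10% in both arms, the half-width of the 95% interval is 1.96 × √(2 × 0.1 × 0.9/46) = 0.123, about 12 points. It would be too strong to infer that 92 neonates could rarely exclude any smaller excess. Enumerating all outcomes at 10% in both arms, and giving Newcombe then Wald intervals:

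- an excess of 12 points is excluded in 45% to 51% of trials;
- an excess of 10 points in 30% to 39%;
- an excess of 5 points in 10% to 14%.

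At 5% in both arms, an excess of 10 points is excluded in 43% to 62%.

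**Continuous measures.** Much of what is recorded is continuous: saturation, heart rate, temperature, respiratory rate. For a two-sample t-test with 46 per arm, 80% power is reached at 0.59 SD (normal approximation: (1.96 + 0.84) × √(2/46) = 0.58 SD). The 95% interval for a mean difference has half-width 1.96 × √(2/46) = 0.41 SD. A difference of moderate size can therefore be detected or excluded.

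**What the text commits to.** The arithmetic shows that a non-significant result on an uncommon event would be weak evidence. For that to be an error in this protocol, the protocol would have to say that it will draw the stronger conclusion. Set against the text:

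- Item 9 says the data will be analysed for differences. It names no test, p-value, null hypothesis or decision rule. Estimating the difference with its interval is one ordinary way of doing what it says.
- The word safety occurs in the title and as the reason for continuous oximetry. Neither place links it to a non-significant comparison.
- The title declares a pilot, which announces that estimates will be imprecise.

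**The case for a change.** The strongest case for the concern is that it does not complain of missing detail: the aim that the protocol does state is a detection question, while the title asks whether the practice is safe. A pilot, on this view, should estimate with an interval, and nothing in the protocol guards a reader against taking a null result as reassurance. A few sentences in item 9 would supply that guard at no cost in neonates or procedures.

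Part of this stands. Absence of a detected difference is not evidence of safety, the power figures are correct under their assumptions, and a caution to that effect would do no harm. But it does not establish a fault. The step from no difference to safe is supplied by the reader; the protocol does not take it. The remedy would consist of a named main measure, an estimate with its interval, descriptive status for the rest, perhaps a margin, and a rule of interpretation. Those are matters commonly left to a statistical analysis plan. One may exist, and the statistician's calculation of 92 rests on inputs that cannot be seen here; it may already have used a particular outcome or margin. Without those items, what remains is a preference about the word differences in one plain-language sentence.

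**Conclusion.** The concern does not hold. Item 9 is compatible with a sound analysis, including estimation with confidence intervals, and the protocol nowhere commits itself to treating a non-significant result as proof of safety. The figures behind the worry, such as 18% to 27% power for 10% against 20%, rest on three assumptions that the protocol does not make: 46 per arm, a binary adverse event as the measure, and a control rate of about 10% or less. Under other equally open assumptions the picture is better: 77% to 84% power for 30% against 60%, or 80% power at about 0.59 SD for a continuous measure. The general caution applies when the results are interpreted, above all for uncommon events. This verdict rests on the protocol alone; it would change if the analysis plan or a report stated that a non-significant difference will be read as safety.
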